In the event that study subjects are discharged before the end of follow up, they will be requested to present to the RACC or the outpatient COVID research clinic for the remaining study time points, where a research nurse will conduct the study visit and obtain swab samples. Subjects will be strongly discouraged from using taxi or rideshare services to return for outpatient visits. Parking vouchers (purchased with study funds) will be provided to subjects to cover out of pocket cost of parking. For subjects who are unable to return to MGH for outpatient visits, home visits will be made an option through the established vendor. Subjects who confirm inability to return to MGH for outpatient visits and do not live within the service area of the established vendor will be excluded from the study (under inclusion criteria #5).

Upon completion of the Day 14 visit, subjects will be instructed their study participation has ended and will be referred back to their care team for any necessary clinical follow-up, inclusive of additional clinical COVID PCR testing, as needed. **Subjects will be instructed to follow the clinical recommendations and CDC guidelines provide at time of hospital discharge by their treating team regarding COVID-19 vaccination timing and reminded that study participation should not impact these clinical recommendations. Although there is a possibility of interface of pegylated interferon lambda with the immune response to COVID-19 vaccines and vaccination is recommended to be delayed for 2 weeks after last dose of peginterferon lambda (given potential to interfere with vaccine effectiveness)**

this is not expected to impact clinical eligibility for vaccination due to the short duration of study participation and timing of last dose at day 7.

Female subjects of childbearing potential will be instructed to self-report a pregnancy that occurs within 30 days of their day 7 dose, but study staff will not directly query subjects regarding pregnancy after Day 14.

For those participants who require home visits, study drug administration and sample collections will be conducted by the appropriately trained and credentialed staff from the vendor. The location of the study visit (home vs. RACC) will be captured in the study source.

Blood draws will be performed by qualified personnel at the request of study staff. Research coordinators will never perform blood draws. Blood samples may be drawn from arterial or central lines or PICC catheters and will not be drawn from peripheral lines, except at the time of placement of a new peripheral line. Blood samples for research purposes will be drawn alongside clinical samples, wherever possible. Alternatively, lab results obtained close to study time points for clinical purposes may be used, if available.

Unscheduled Visits

Additional unscheduled assessments may be performed at the discretion of the investigator.

Early Termination Visit

In the event a subject terminates the study prior to completion of the 14 day follow up period, the Early Termination (ET) visit should be scheduled as soon as possible. The early termination visit procedures are outlined in [Appendix 2](#) and mirror the day 14 visit but without research archive sample collection.

VII. Adverse Events and Toxicity Management

Definition of Adverse Events, Adverse Reactions and Serious Adverse Events

Adverse Event

An adverse event (AE) is any untoward medical occurrence in a clinical study subject administered a medicinal product, which does not necessarily have a causal relationship with the treatment. An AE can therefore be any unfavorable and/or unintended sign, symptom, or disease temporally associated with the use of a medicinal product, whether or not considered related to the medicinal product. AEs may also include pre- or post-treatment complications that occur as a result of protocol specified procedures, overdose, drug abuse/misuse reports, or occupational exposure. Preexisting events that increase in severity or change in nature during or as a consequence of participation in the clinical study will also be considered AEs.

An AE does not include the following:

- Medical or surgical procedures such as surgery, endoscopy, tooth extraction, and transfusion.
- The condition that led to the procedure may be an adverse event and must be reported

- Pre-existing diseases, conditions, or laboratory abnormalities present or detected before the Screening visit that do not worsen
- Situations where an untoward medical occurrence has not occurred (e.g., hospitalization for elective surgery, social and/or convenience admissions)
- Overdose without clinical sequelae
- Any medical condition or clinically significant laboratory abnormality with an onset date before the consent form is signed and not related to a protocol-associated procedure is not an AE. It is considered to be pre-existing and should be documented on the medical history case report form (CRF)

Serious Adverse Event

A **serious adverse event** (SAE) is defined as an event that, at any dose, results in the following:

- Death
- Life-threatening (Note: The term “life-threatening” in the definition of “serious” refers to an event in which the subject was at risk of death at the time of the event; it does not refer to an event that hypothetically might have caused death if it were more severe)
- In-patient hospitalization or prolongation of existing hospitalization
 - Hospitalization for an elective procedure is not considered an SAE for the purposes of this study
- Persistent or significant disability/incapacity
- A congenital anomaly/birth defect
- A medically important event or reaction: such events may not be immediately life-threatening or result in death or hospitalization but may jeopardize the subject or may require intervention to prevent one of the other outcomes constituting SAEs. Medical and scientific judgment must be exercised to determine whether such an event is a reportable under expedited reporting rules.

Examples of medically important events include:

- intensive treatment in an emergency room or at home for allergic bronchospasm
- blood dyscrasias or convulsions that do not result in hospitalization
- development of drug dependency or drug abuse

Clinical Laboratory Abnormalities and Other Abnormal Assessments as Adverse Events or Serious Adverse Events

Laboratory abnormalities without clinical significance are not recorded as AEs or SAEs. However, laboratory abnormalities (e.g., clinical chemistry, hematology) that require medical or surgical intervention or lead to investigational medicinal product (IMP) interruption, modification, or discontinuation must be recorded as an AE, as well as an SAE, if applicable. In addition, laboratory or other abnormal assessments (e.g., vital signs) that are associated with signs and/or symptoms must be recorded as an AE or SAE if they meet the definition of an AE or SAE as described above. If the laboratory abnormality is part of a syndrome, record the syndrome or diagnosis (e.g., anemia), not the laboratory result (i.e., decreased hemoglobin).

Assessment of Adverse Events and Serious Adverse Events

The investigator or qualified sub investigator is responsible for assessing AEs and SAEs for causality and severity, and for final review and confirmation of accuracy of event information

and assessments.

Assessment of Causality for Study Drugs and Procedures

Assessment of relatedness will be made by a physician investigator with respect to the stage of the trial that the subject is in (screening, on-treatment, post-treatment) and further with respect to whether the event was related to Lambda/placebo where applicable. The following will be used to assess the relationship of the adverse event to the use of Lambda/placebo:

1. Probably related

- Event or laboratory test abnormality, with reasonable time relationship to drug intake
- Unlikely to be attributed to disease or other drugs
- Response to withdrawal clinically reasonable
- Rechallenge not required

2. Possibly related

- Event or laboratory test abnormality, with reasonable time relationship to drug intake
- Could also be explained by disease or other drugs
- Information on drug withdrawal may be lacking or unclear

3. Unlikely related

- Event or laboratory test abnormality, with a time to drug intake that makes a relationship improbable (but not impossible)
- Disease or other drugs provide plausible explanations

4. Unrelated

- Event assessed as having no reasonable possibility of being related to study drug

5. Unclassified

- Event or laboratory test abnormality
- More data for proper assessment needed, or additional data under examination
- Report suggesting an adverse reaction
- Cannot be judged because information is insufficient or contradictory
- Data cannot be supplemented or verified

The relationship of an AE or SAE to study procedures (e.g., invasive procedures such as venipuncture or biopsy) should be assessed using the following considerations:

- **No:** Evidence exists that the adverse event has an etiology other than the study procedure
- **Yes:** The adverse event occurred as a result of protocol procedures, (e.g., venipuncture)

Extra consideration will be made regarding fever as an adverse event. Fever is noted as a less common (<10%) potential side effect of Lambda, as well as a common expected symptom of COVID-19 infection. To best distinguish between fever associated with COVID-19 and Lambda treatment emergent or exacerbation of fever, study investigators will adjudicate suspected causality by reviewing time elapsed

between Lambda administration and onset/exacerbation of fever. We acknowledge that this distinction cannot be made with complete accuracy.

Assessment of Severity

The severity grading of AEs will be assessed as Grade 1, 2, 3, 4, or 5 according to the Common Terminology Criteria for Adverse Events (CTCAE) Version 4.03, which can be found at http://evs.nci.nih.gov/ftp1/CTCAE/CTCAE_4.03_2010-06-14_QuickReference_8.5x11.pdf.

For AEs associated with laboratory abnormalities, the event should be graded on the basis of the clinical severity in the context of the underlying conditions; this may or may not be in agreement with the grading of the laboratory abnormality.

The distinction between the seriousness and the severity of an adverse event should be noted. Severe is a measure of intensity; thus, a severe reaction is not necessarily a serious reaction. For example, a headache may be severe in intensity, but would not be classified as serious unless it met one of the criteria for serious events listed above.

Reporting of Adverse Events

The Principal Investigator ([name]) will be immediately notified of any adverse events. These will be documented in detail in the Adverse Events Tracking Log and submitted each year at the time of continuing review. Adverse events will be reported to the PHRC as described in the PHRC policy on Unanticipated Problems Involving Risks to Subjects or Others.

VIII. Statistical Considerations

Data Analysis

All subjects will be included in the primary intention-to-treat analysis as well as the analyses of secondary outcomes and observed safety events. The primary analysis will compare the proportion of subjects who are PCR negative at post-treatment Day 7 between subjects receiving Lambda vs. standard of care using Fisher's exact test, and the difference between the treatment groups will be estimated using the difference in proportions. Subjects who die during follow up will be considered not to have achieved viral clearance, for the purposes of statistical analysis. Subjects who are lost to follow up will be removed from the analysis, since we consider loss to follow up as being unrelated to our outcome of interest. A key secondary analysis will compare the mean change in quantitative PCR from baseline to Day 7 in the treatment group and placebo group using a two-sample t-test. This analysis will likely have more power to detect a treatment effect compared to the PCR negative analysis since a continuous outcome will be used.

Additional secondary analyses will compare the proportion of subjects who are PCR negative at post-treatment Days 3, 5, and 14 and the mean magnitude of viral load reduction using the same approach at Day 7. In addition, the time to PCR negativity will be compared using a log-rank test, and the difference between the treatment groups will be estimated using a Cox proportional hazards model. To compare changes in symptom scores over time, a linear mixed model will be used to estimate the difference in the change with time between the two treatment groups at each of the post-baseline timepoints. For safety endpoints, the proportion of subjects who experience each type of event will be compared between the Lambda vs. standard of care groups at Day 14 using Fisher's exact test. Additional analysis

will compare proportions of hospitalized subjects who experience progression of disease as reflected by transfer to ICU or intubation, and the length of stay among hospitalized subjects will be compared using the log-rank test. Subjects who die will be analyzed as having a length of stay censored at one day past the last follow-up date. Hence, subjects who die will be considered as having a greater length of stay than subjects who remain alive for the duration of the study. Statistical analyses will be completed using SAS (SAS Institute 2011, Version 9.4, Cary, NC).

Sample size and power calculation:

This is a pilot study to assess the ability of Lambda to increase the proportion of subjects with PCR negativity at Day 7 compared to standard of care (placebo group) as a primary endpoint. We anticipate that no subjects in the standard of care arm will be PCR negative at Day 7, and we anticipate that 50% of subjects in the Lambda arm will be PCR negative at Day 7.

The treatment will be considered for further study if the proportion of subjects who achieve PCR negativity will be 30% higher at Day 7 in the Lambda arm compared to the standard of care arm. This would correspond to 3/10 subjects in the Lambda arm if 0/10 subjects were PCR negative in the standard of care (placebo) arm. Assuming 50% of subjects will be PCR negative, we have a 94% chance of observing 3 or more subjects who are PCR negative at Day 7. This shows that our sample size of 10 subjects per group is sufficient to have a reasonable chance to support further study given the proposed treatment effect. Additionally, demonstration of a reduction in viral load relative to the placebo arm will be factored into decisions to pursue further trials.

IX. References

3. Loutfy MR et al. Interferon alfacon-1 plus corticosteroids in severe acute respiratory syndrome: A preliminary study. *JAMA* 2003 Dec 24/31; 290:3222-8.

Appendices

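### The lost-to-follow-up rule is not tied to the Day 7 swab, so applied as written it drops subjects whose primary outcome is already known

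*Combined protocol and SAP*

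**What the plan says.** All of the analysis text is in Section VIII of the combined protocol and SAP.

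- Data Analysis opens with the population: "All subjects will be included in the primary intention-to-treat analysis as well as the analyses of secondary outcomes and observed safety events".
- After the primary Fisher test and a rule that counts deaths as not cleared, it adds: "Subjects who are lost to follow up will be removed from the analysis, since we consider loss to follow up as being unrelated to our" [endpoint, named in the singular]. It attaches no definition of loss, no time point and no endpoint.
- The secondary analyses come later in the same section. They include time to PCR negativity, safety proportions, and a length-of-stay comparison: "the length of stay among hospitalized subjects will be compared using the log-rank test". A length-of-stay censoring rule is given for deaths; none is given for loss. No censoring rule is stated for time to negativity.
- The sample size text sets a 30-point difference at Day 7 as the mark for further study: "This would correspond to 3/10 subjects in the Lambda arm if 0/10 subjects were PCR negative" in the placebo arm. It adds that viral load reduction will also be weighed.

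Section VI fixes the length of follow-up. The Early Termination Visit text begins "In the event a subject terminates the study prior to completion of the 14 day follow up period", so follow-up extends a week past the primary assessment. After discharge, subjects have to come back or be visited at home: "In the event that study subjects are discharged before the end of follow up, they will be requested to present to the RACC" or an outpatient clinic.

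**The concern.** The rule acts on the subject, not on the missing value. Follow-up lasts 14 days, so a subject who gives a Day 7 swab and cannot be reached for the Day 14 visit is lost to follow-up. As written, that subject leaves the primary analysis although the primary outcome is on file. The stated justification, that loss is unrelated to outcome, bears on values that were never observed. Even if it is true, it gives no reason to discard one that was.

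The rule also contradicts the paragraph's own first sentence. Two analysts following the same paragraph could use different denominators for the primary comparison. With 10 subjects per arm, one subject can decide on which side of the threshold the trial falls, and here that would depend on something that happened after the endpoint was measured.

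**Working it through.** **Inputs from the plan (Section VIII, sample size text):** 10 per arm; Day 7 PCR negativity 50% on Lambda and 0% on placebo; threshold a difference of at least 30 points; stated chance of meeting it 94%.

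**Assumptions, because the documents give no figure:** each subject is lost after the Day 7 swab, at random and independently, with probability q = 5%, 10% or 20%. Where Fisher power is quoted, a two-sided 5% level.

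**1. The plan's own figure.** P(X ≥ 3) for X ~ Binomial(10, 0.5) = 1 − (1 + 10 + 45)/1024 = 968/1024 = 94.5%. The stated 94% is reproduced.

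**2. Deleting one subject whose Day 7 result is known.**

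| Full data | Deleted subject | After deletion |
|---|---|---|
| 3/10 vs 0/10 = 30 points, met | Lambda, negative | 2/9 vs 0/10 = 22.2 points, not met |
| 4/10 vs 1/10 = 30 points, met | Lambda, negative | 3/9 vs 1/10 = 23.3 points, not met |
| 4/10 vs 1/10 = 30 points, met | Placebo, positive | 4/10 vs 1/9 = 28.9 points, not met |
| 3/10 vs 1/10 = 20 points, not met | Placebo, negative | 3/10 vs 0/9 = 30 points, met |

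The last three rows need a PCR-negative placebo subject, which the plan does not expect.

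**3. Chance of meeting the threshold under 50% vs 0%.** Let a ~ Binomial(10, 0.5) be the Lambda negatives, r ~ Binomial(a, q) the negatives lost and s ~ Binomial(10 − a, q) the positives lost. The threshold is met if (a − r)/(10 − r − s) ≥ 0.30; the placebo proportion stays at 0. Exact enumeration gives:

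| q | Threshold met | Met becomes not met | Not met becomes met | Decision differs from full data |
|---|---|---|---|---|
| 0 | 94.5% | – | – | – |
| 5% | 92.6% | 2.0% | 0.0% | 2.0% |
| 10% | 90.4% | 4.2% | 0.02% | 4.2% |
| 20% | 86.4% | 8.3% | 0.16% | 8.4% |

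If only PCR-negative subjects are lost, at 10% or 20%, the chance is 90.1% or 83.6%.

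**4. Fisher's test.** It can move either way. 5/10 vs 0/10 gives p = 0.033; losing one Lambda negative and one placebo subject gives 4/9 vs 0/9, p = 0.082. Conversely, 4/10 vs 0/10 gives p = 0.087; losing one Lambda positive gives 4/9 vs 0/10, p = 0.033. Power is 62.3% with all swabs kept, and 62.8%, 58.7% or 47.6% at q = 5%, 10% or 20%.

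**The case against.** The strongest reply is that nobody would apply the sentence this way. A subject with a Day 7 swab is not lost for a Day 7 endpoint, and the rationale given is a missing-data rationale, which suggests that only absent results were meant. Loss after Day 7 means missing a single visit. The protocol provides home visits and an early termination visit with a swab, so the loss rate may be low. This supports calling the remedy a clarification, but it does not remove the defect. The sentence carries no such limit, the neighbouring death rule also runs over the whole of follow-up, and the opening sentence points the other way.

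Three stronger readings are tempting and are not supported.

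- A reader might infer that the plan orders the deletion of completed hospital stays, early swabs and adverse events of subjects later lost. The rule speaks of one analysis and one outcome of interest, stands directly after the primary analysis, and precedes the secondary ones. The opening sentence expressly keeps all subjects in the secondary and observed-safety analyses. For those endpoints the fault is unclear scope and an internal conflict. A shift in length of stay could be calculated only from an assumed stay distribution and loss rate, and would not by itself show bias between arms.
- A reader might infer that the decision will flip. That needs a result at or near the threshold. The threshold marks a treatment to be considered for further study, with viral load weighed as well, so it is not a mechanical gate.
- A reader might take the chance that at least one known result is discarded, 1 − (1 − q)^20 = 64%, 88% or 99%, as the size of the harm. It counts any removal; the decision changes in only 2% to 8% of trials. Nor is the harm uniform: at 5% loss, Fisher power rises slightly.

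**Conclusion.** The point holds for the primary endpoint. The rule as written discards observed Day 7 results and contradicts the intention-to-treat statement in the same paragraph. One deletion can move a result at the threshold across it. Under the plan's own rates, the chance of meeting the threshold falls from 94.5% to 92.6%, 90.4% or 86.4%, and the decision differs from the full-data decision in 2.0%, 4.2% or 8.4% of trials.

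These figures rest on assumed random losses of 5%, 10% and 20% after Day 7, on applying the sentence literally, and on treating the 30-point difference as the sole criterion. For time to negativity, length of stay and safety, the finding is limited to a rule of undefined reach that conflicts with the opening sentence. How to treat a Day 7 swab that was never taken is a separate question. The change should be made, because it is simple and has no real downside.

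**What to change.** Replace the lost-to-follow-up sentence in Section VIII, Data Analysis, with:

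> Each analysis uses every outcome observed before loss to follow-up. A subject with a Day 7 swab stays in the Day 7 analysis whatever happens later; only subjects without a Day 7 swab are treated as missing for the primary endpoint. Time to PCR negativity is censored at the last swab, length of stay uses the discharge date when known and is otherwise censored at last contact, and all adverse events observed before loss are counted.

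Then reconcile this with the opening sentence of Data Analysis. In particular, state whether the safety denominator is all randomized or all dosed subjects, since that sentence says only that all subjects are included.

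The cost is a wording change to the analysis section, with no extra patients, visits or data. It should be settled before outcomes by arm are seen, so that the denominator is not chosen afterwards.

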- To assess the efficacy of Lambda (180 mcg SC injections) vs. saline placebo injection in inducing PCR negativity at days 3, 7 and 14 among hospitalized subjects with symptomatic COVID-19 infection
- To assess the efficacy of Lambda (180 mcg SC injections) vs. saline placebo injection in inducing symptomatic improvement in subjects with COVID-19 infection, assessed by daily symptom questionnaire
- To assess the efficacy of Lambda (180 mcg SC injections) vs. saline placebo injection in improving clinical outcomes (death, ICU stay, intubation) in subjects hospitalized with COVID-19 infection
- To evaluate the safety and tolerability of Lambda (180 mcg SC injections) vs. saline placebo injection

III. Study Design

This is a prospective randomized trial to assess the antiviral efficacy of Lambda (180 mcg SC injection) vs. standard of care in up to 20 subjects hospitalized with COVID-19 infection.

Visit schedule

After referral by the care team and informed consent, and once the subject is confirmed as COVID-19 positive on clinical testing, patients will have initial clinical lab testing performed during baseline (visit 1). After confirmation of inclusion criteria, patients will be randomized 1:1 to receive the first dose of Lambda or saline placebo at the baseline visit (visit 1). Nasal swabs for PCR analysis will be collected for all subjects on Days 3, 7 and 14. An optional Day 5 nasal swab collection will occur only for subject who remain hospitalized on Day 5. On day 7, subjects in the treatment arm will receive a second Lambda injection and subjects in the control arm will receive a second saline placebo injection. On Day 14, subjects will undergo laboratory measurements to confirm CBC and LFT values are within safe parameters. Research blood will be collected and stored for future testing to measure levels of pro-inflammatory cytokines (e.g. IFN- γ , IL-6, IP-10, MCP-1, TNF- α). Measurements will be performed using excess blood collected for clinical purposes wherever possible. Subjects will complete a daily symptom questionnaire from screening through Day 14 ([Appendix 5](#)).

Administration of Treatment

Upto an initial 30 hospitalized patients will be enrolled (consented), with a goal of 20 subjects randomized 1:1 to receive either Lambda 180 mcg SC injections or saline placebo injections.

Administration of first dose Lambda/placebo in relation to initial COVID-19 symptom onset will be documented in all subjects.

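### Day 5 PCR negativity is compared between arms in all subjects, but only those still in hospital are swabbed that day, so randomisation does not protect the comparison

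*Combined protocol and SAP*

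**What the plan says.** The Data Analysis text of Section VIII defines the population broadly: "All subjects will be included in the primary intention-to-treat analysis as well as the analyses of secondary outcomes". It then plans this comparison: "Additional secondary analyses will compare the proportion of subjects who are PCR negative at post-treatment Days 3, 5, and 14". The method is the one used at Day 7, namely Fisher's exact test with a difference in proportions. The same sentence adds "the mean magnitude of viral load reduction using the same approach at Day 7", which leaves unclear whether viral load is also to be tested at Day 5.

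The visit schedule in Section III limits who has Day 5 data: "An optional Day 5 nasal swab collection will occur only for subject who remain hospitalized on Day 5". The Day 5 paragraph of Section VI and the footnote to the Appendix 2 table agree. Swabs are scheduled for every subject only on Days 3, 7 and 14, and the secondary objective in Section II names those same three days.

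Section VIII has two rules for incomplete outcomes. For deaths: "Subjects who die during follow up will be considered not to have achieved viral clearance". For dropouts: "Subjects who are lost to follow up will be removed from the analysis". Section VI keeps discharged subjects in the study through clinic or home visits. Two other planned analyses bear on the point: "the length of stay among hospitalized subjects will be compared using the log-rank test", and "the time to PCR negativity will be compared using a log-rank test".

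**The concern.** A subject who goes home on Day 4 is neither dead nor lost to follow-up, yet has no Day 5 result. The analyst must either drop that subject or count the subject as not negative, and the plan does not say which.

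The first dose is given at baseline, so being an inpatient on Day 5 is a status that arises after treatment starts. The plan compares length of stay between arms, so it allows that treatment may change that status. A Day 5 difference would be read as a randomised treatment effect although part of it may reflect who was still in hospital.

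Time to PCR negativity has a related gap. If Day 5 swabs count, clearance can be detected earlier in inpatients than in discharged subjects, for whom the next swab is Day 7.

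**Working it through.** **The plan's own figure.** The plan gives no operating figure for Day 5. Its only one is the 94% chance of at least 3 of 10 negatives at Day 7 when the true rate is 50%: 1 - (1 + 10 + 45)/1024 = 0.945. This reproduces and is unaffected by the Day 5 issue.

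**Inputs.** From the documents: 10 subjects per arm, and anticipated Day 7 negativity of 50% vs 0%. Assumed, because the documents give none: Day 5 negativity, discharge rates, and a two-sided alpha of 0.05.

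**Formula.** Let p be true Day 5 negativity, and let dc and dn be the shares of cleared and uncleared subjects discharged before Day 5.

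- Negativity among inpatients = p(1 - dc) / [p(1 - dc) + (1 - p)(1 - dn)]
- Negativity if unswabbed subjects count as not negative = p(1 - dc)

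**No true effect, p = 0.30 in both arms.** Placebo has dc = dn = 0.3. Its inpatient rate is 0.21/0.70 = 30.0%, with 7.0 of 10 expected to be swabbed.

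| Lambda discharge pattern | Lambda inpatient rate | Expected swabbed (Lambda) | Difference, inpatients | Difference, unswabbed = not negative |
|---|---|---|---|---|
| (i) dc 0.7, dn 0.3 | 0.09/0.58 = 15.5% | 5.8 | -14.5 points | 9% - 21% = -12 |
| (ii) dc 0.3, dn 0.6 | 0.21/0.49 = 42.9% | 4.9 | +12.9 points | 21% - 21% = 0 |
| (iii) dc 0.6, dn 0.6 | 0.12/0.40 = 30.0% | 4.0 | 0 points | 12% - 21% = -9 |

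The true difference is zero in every row. Which counting rule does the damage depends on the discharge pattern.

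**Same discharge pattern in both arms (dc 0.7, dn 0.3).** The odds in each arm are multiplied by the same factor, (1 - dc)/(1 - dn), so the odds ratio and the null are preserved. The difference in proportions is not:

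- 30% vs 30% becomes 15.5% vs 15.5%; a null stays null.
- 50% vs 30% becomes 30% vs 15.5%: 20 points shrink to 14.5 (odds ratio 2.33 before and after).
- 70% vs 50% becomes 50% vs 30%: 20 points, unchanged.
- 80% vs 60% becomes 63% vs 39%: 20 points grow to 24 (odds ratio 2.67 before and after).
- 50% vs 0% becomes 0.15/0.50 = 30% vs 0%: 50 points shrink to 30.

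**Fisher's test, by exact enumeration.** The number swabbed per arm is binomial (10, share still in hospital), negatives are then binomial, and rejection is at two-sided p ≤ 0.05.

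- No true effect at 30%: 1.2% with all swabbed, 1.8% under (i), 3.0% under (ii), 0.4% under the same-pattern case.
- 50% vs 0%: power 62% with all 20 swabbed, 36% if 30% are discharged regardless of PCR status, 8% under the same-pattern case.
- 50% vs 30%: power about 5% even with all 20 swabbed.

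**The case against.** The strongest reply concerns size. The null illustrations use 30% negativity, while the sample size text expects no placebo subject to be negative even at Day 7. With the same discharge patterns, (i) and (ii) give -5.5 and +6.3 points at 10% negativity, -2.8 and +3.4 at 5%, and exactly 0 at 0%. A spurious difference also requires treatment to change how discharge relates to PCR status. No section says that PCR status influences discharge, and pattern (ii) has no stated rationale. Noise exceeds the bias as well: at the expected inpatient numbers the standard error of the difference is about 23 points in (i), from √(0.155×0.845/5.8 + 0.3×0.7/7.0), and about 28 points in (ii).

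This stands as a limit on magnitude, and it is why the point is minor. It does not remove the problem. At the plan's own 50% vs 0% a real effect can still be attenuated from 50 points to 30, and the rule for unswabbed subjects is missing whatever the rates.

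A second reply is that readers will take Day 5 to mean inpatients only. Section VIII says all subjects. On the inpatient reading it would still compare groups selected after randomisation, without a caveat.

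A third reply is that other repairs exist, such as labelling the test inpatient-only with a stated counting rule, or using interval-censored methods for time to negativity so that no swab is discarded. These would close the gap in the text. Labelling alone would not restore the protection of randomisation.

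**Conclusion.** The concern holds, at minor severity. As written, the plan tests a Day 5 difference in all subjects when data can exist only for those still in hospital, and neither of its missing-outcome rules applies to subjects discharged earlier. That conclusion rests on the text alone and is firm.

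The amount of distortion is not known. Under the assumed rates it runs from none (discharge unrelated to PCR status, inpatients only) to roughly 13 to 15 points either way when 30% are negative in both arms. It is smaller at lower negativity. The likely harm is a misleading estimate rather than a false significant result. The primary Day 7 endpoint and the 30-point rule for further study are unaffected.

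**What to change.** In Section VIII:

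- Remove Day 5 from the between-arm tests of PCR negativity, and from those of viral load if that was intended.
- Report Day 5 results descriptively among inpatients, giving the number swabbed and the number discharged in each arm.
- Define time to PCR negativity from the swabs scheduled for everyone (Days 3, 7 and 14), and say how an Early Termination swab counts.

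The cost is one or two sentences. Day 5 appears in no objective, so nothing promised is lost and Section VIII then matches Section II. The swab can still be collected. The downside is a slight loss of timing detail for inpatients.
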